5.7.3. Additional Safety Assessments**5.7.3.1. Clinical Laboratory Tests**

Clinical laboratory tests will be displayed for the participants included in the safety analysis set.

Descriptive statistics and graphical displays will be presented for selected chemistry and hematology, laboratory tests at scheduled time points.

Change from baseline through Week 24 and Week 52 will be summarized for chemistry and hematology tests and displayed by intervention group. A box plot of change from baseline through Week 24 and Week 52 will be provided.

- **Hematology assessments** will include but are not limited to the following: hemoglobin, hematocrit, platelet count, total and differential White Blood Cell count, B-cell analysis.
- **Blood chemistry assessments** will include but are not limited to the following: chemistry panel (total and direct bilirubin, alanine aminotransferase, aspartate aminotransferase, alkaline phosphatase, albumin, total protein, calcium, phosphate, sodium, potassium, chloride, blood urea nitrogen/urea, and creatinine).

The National Cancer Institute's Common Terminology Criteria for Adverse Events (NCI-CTCAE; version 5.0) will be used in the summary of laboratory data (Grade 0-4). The proportion of participants with post-baseline values by maximum toxicity grade for clinical laboratory tests will be summarized by study intervention group. Participants with toxicity grades ≥ 2 will be listed.

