5.2. Main Study Exclusion Criteria

Any potential participant who meets any of the following criteria will be excluded from participating in the study:

1. Current or history of, severe, progressive, or uncontrolled renal disease, with the exception of active LN.
2. Current or history of, severe, progressive, or uncontrolled hepatic, hematological, gastrointestinal, pulmonary, cardiac, or neurological disease, either related or unrelated to SLE (or, in the investigator's opinion, any other concomitant medical condition that places the participant at risk by participating in this study).
3. Anticipated to require dialysis within 6 months.
4. Transplanted organ (with the exception of a corneal transplant performed >12 weeks before screening).
5. Comorbidities (other than LN, eg, asthma, chronic obstructive pulmonary disease) which have required 3 or more courses of systemic glucocorticoids within the previous 12 months.
6. Has any unstable or progressive manifestation of SLE (eg, lupus cerebritis, optic neuritis, transverse myelitis, psychosis, uncontrolled seizures, systemic vasculitis, rapidly progressive glomerulonephritis, end-stage renal disease], pulmonary hemorrhage, myocarditis) that is likely to warrant escalation in therapy beyond permitted background medications. Participants requiring renal hemodialysis or peritoneal dialysis are also excluded.
7. Criterion modified per Amendment 3.
 - 7.1. Isolated or predominant Class V LN (ie, without coexistent Class III or IV nephritis).

8. Has other inflammatory diseases that might confound the evaluations of efficacy, including but not limited to RA, PsA, RA/lupus overlap, psoriasis, Crohn's disease, or active Lyme disease.
9. Has a history or suspected occurrence of drug-induced lupus.
10. Has a history of catastrophic antiphospholipid syndrome (APS). Subjects with a history of non-catastrophic APS must be adequately controlled with anticoagulation and/or anti-platelet therapy in accordance with local guidelines. The suitability of the subject to participate in the study must be discussed with the medical monitor and/or sponsor before the subject is randomized.
11. Has inherited complement deficiency or combined variable immunodeficiency.

Screening laboratory tests

12. eGFR <30 ml/min per 1.73m².
13. Absolute neutrophil count <1.0 ×10⁹/L.
14. Platelet count <75 ×10⁹/L.
15. Criterion modified per Amendment 1.
 - 15.1 Hemoglobin <8.0 g/dL.

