9.4.6. Safety Analyses

All safety analyses will be analyzed using the SAS population (refer to Section 9.3 for definition).

Adverse Events

The verbatim terms used in the eCRF by investigators to identify AEs will be coded using the Medical Dictionary for Regulatory Activities. Any AE occurring at or after the initial administration of study intervention is considered to be treatment-emergent. All reported treatment-emergent AEs will be included in the analysis. For each AE, the percentage of participants who experience at least 1 occurrence of the given event will be summarized by intervention group. In addition, comparisons between intervention groups will be provided if appropriate.

The following analyses of AEs will be used to assess the safety of participants:

- Frequency and type of AEs.
- Frequency and type of SAEs.
- Frequency and type of reasonably related AEs as assessed by the investigator.
- Frequency and type of AEs leading to discontinuation of study intervention.
- Frequency and type of infections, serious infections, and infections requiring oral or parenteral antimicrobial treatment.
- Frequency and type of AEs temporally associated with an infusion.
- Frequency and type of injection-site reactions.

Summaries, listings, datasets, or participant narratives may be provided through Week 24 and Week 60 by treatment intervention, for the above AEs, deaths, and severe AEs. Selected safety summaries will also be performed for participants of the LTE (Section 9.4.8).

Clinical Laboratory Tests

Laboratory data will be summarized by type of laboratory test over time, and by treatment intervention. CTCAE toxicity grades (specified in the SAP) will be used in the summary of laboratory data. Descriptive statistics will be calculated for each laboratory analyte at baseline and for observed values and changes from baseline at each scheduled timepoint.

The following summaries of clinical laboratory tests will be used to assess participant safety:

- Laboratory parameters and change from baseline in laboratory parameters (hematology and chemistry).
- Summary of maximum CTCAE toxicity grade for postbaseline laboratory values (hematology and chemistry).

Listings of participants with any abnormal postbaseline laboratory values of CTCAE Grade ≥ 2 will also be provided.

Vital Signs

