5.7. Safety Analyses

Early Termination Note: Due to the Sponsor's decision to stop screening of new participants as a result of enrollment challenges, fewer than 60 participants will be enrolled in the study. The end of study will occur after all enrolled participants have completed the Week 20 visit or discontinued study intervention prior to Week 24, and all participants have completed their final efficacy and safety visits per the SoA.

For the CSR, all safety analyses described below will be performed on all available data through the end of study.

All safety analyses will be based on the safety analysis set based on actual intervention received, unless otherwise specified.

For all continuous safety variables, descriptive statistics by intervention group will include the N, mean, SD, median, minimum, and maximum. Categorical variables will be summarized by intervention group using frequency counts and percentages.

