5.7.3.3. Vital Signs and Physical Examination Findings

Continuous vital sign parameters including weight, height, pulse, and blood pressure (systolic and diastolic) will be summarized at each assessment time point. Change from baseline of the vital sign parameters will be summarized for through Week 24 and through Week 60. Descriptive statistics (mean, SD, median, minimum and maximum) will be presented.

Summaries of treatment-emergent abnormal vital signs during intervention, as defined in Table 4, will be provided for participants who had a baseline assessment and at least 1 postbaseline assessment for that vital sign. A listing of participants with treatment-emergent abnormal vital signs will be presented.

Table 4: Abnormal Vital Sign Parameters

Vital Sign	Criteria
Pulse	>130 bpm or <50
Systolic blood pressure	>180 mm Hg or <85 mm Hg
Diastolic blood pressure	>115 mm Hg or <55 mm Hg
Weight	Increase/decrease 10 kg from baseline

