APPENDIX 10: LABORATORY TOXICITY GRADING

The grading scale used for lab assessments is based on ‘Common Terminology Criteria for Adverse Events (CTCAE) v5.0’.

If a laboratory value falls within the grading as specified below but also within the local laboratory normal limits, the value is considered to be normal and will be reset to grade 0.

Pre-baseline measurements will use the same grading ranges as applied to baseline measurements. In case a test has two sets of ranges – one for baseline normal and one for baseline abnormal, the one for baseline normal will be applied for all measurements taken pre-baseline and on baseline.

Text in gray italic in the table is present in the grading scale, but is not applied by Janssen when grading lab data.

CTCAE Term	Grade 1	Grade 2	Grade 3	Grade 4	Janssen implementation notes
Blood and lymphatic system disorders					
Anemia	Hemoglobin (Hgb) <LLN - 10.0 g/dL; <LLN - 6.2 mmol/L; <LLN - 100 g/L	Hemoglobin (Hgb) <10.0 - 8.0 g/dL; <6.2 - 4.9 mmol/L; <100 - 80g/L	Hemoglobin (Hgb) <8.0 g/dL; <4.9 mmol/L; <80 g/L; transfusion indicated	Life-threatening consequences; urgent intervention indicated	Clinical signs and symptoms are not taken into consideration for grading.
Leukocytosis	-	-	>100,000/mm ³ ; >100 x 10e9 /L	Clinical manifestations of leukocytosis; urgent intervention indicated	Clinical signs and symptoms are not taken into consideration for grading; Added ranges in SI unit (x 10e9 /L)
Investigations					
Activated partial thromboplastin time prolonged	>ULN - 1.5 x ULN	>1.5 - 2.5 x ULN	>2.5 x ULN; bleeding	-	Clinical signs and symptoms are not taken into consideration for grading.
Alanine aminotransferase increased	>ULN - 3.0 x ULN if baseline was normal; 1.5 - 3.0 x baseline if baseline was abnormal	>3.0 - 5.0 x ULN if baseline was normal; >3.0 - 5.0 x baseline if baseline was abnormal	>5.0 - 20.0 x ULN if baseline was normal; >5.0 - 20.0 x baseline if baseline was abnormal	>20.0 x ULN if baseline was normal; >20.0 x baseline if baseline was abnormal	Ranges defined for "abnormal baseline" are applied only if baseline > ULN. If baseline < LLN, then ranges for "normal baseline" are applied.

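### For laboratory tests graded on fixed or normal-range limits, the maximum-grade table and the Grade 2 or higher listing do not show baseline grade, so abnormalities that eligibility allows at entry are counted alongside new ones

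*SAP*

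**What the plan says.** Protocol 9.4.6 names the analysis as "Summary of maximum CTCAE toxicity grade for postbaseline laboratory values (hematology and chemistry") and adds "Listings of participants with any abnormal postbaseline laboratory values of CTCAE Grade" 2 or higher. SAP 5.7.3.1 carries both out: "The proportion of participants with post-baseline values by maximum toxicity grade for clinical laboratory tests will be summarized by study intervention group", plus the same listing. Maximum toxicity grade is also a safety endpoint in Protocol Section 3 and SAP 1.1. It survives early termination, because SAP 5.7 says: "For the CSR, all safety analyses described below will be performed on all available data through the end of study".

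The entry limits are in Protocol 5.2. Exclusions include "Hemoglobin <8.0 g/dL", "Absolute neutrophil count <1.0" x10^9/L, platelets below 75 x10^9/L, eGFR below 30, and ALT or AST at 3 x ULN or above. There is no limit for albumin or lymphocytes.

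The grade limits are in SAP Appendix 10. Grade 2 anemia is "Hemoglobin (Hgb) <10.0 - 8.0 g/dL". Grade 2 neutropenia is 1.0 to below 1.5 x10^9/L, and Grade 1 thrombocytopenia is 75 x10^9/L up to the lower limit of normal (LLN). ALT, AST, alkaline phosphatase, GGT and bilirubin have separate ranges, expressed as multiples of baseline, for participants whose baseline is above the upper limit of normal (ULN). The appendix grades baseline and pre-baseline values as well.

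**The concern.** The grade table is the summary a reader turns to for laboratory toxicity by arm. For tests graded on absolute, LLN or ULN limits, it cannot separate a participant who reached Grade 2 on study from one who was Grade 2 at randomization and stayed there.

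Some of these abnormalities are foreseeable at entry. The trial has a stratum with UPCR of 3 mg/mg or more, which the SAP labels nephrotic proteinuria, and albumin has no entry limit.

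Two consequences follow. A real difference in new abnormalities shrinks in relative terms once the same background share is added to both arms. And with fewer than 60 participants, a chance difference in entry status appears as a difference in maximum grade.

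**Working it through.** The plan gives no numerical claim to reproduce here. The check has three parts.

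**1. Grade a participant whose entry value never changes** (entry limits from Protocol 5.2, grades from SAP Appendix 10).

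| Test | Permitted entry value, unchanged | Grade reported | Listed |
|---|---|---|---|
| Hemoglobin | 8.0 or 9.5 g/dL | 2 | yes |
| Neutrophils | 1.0 or 1.4 x10^9/L | 2 | yes |
| Platelets | 75 x10^9/L | 1 | no |
| Albumin | 2 to below 3 g/dL (no entry limit) | 2 | yes |
| ALT or AST | 2.9 x ULN | 0 (2.9/2.9 = 1.0 x baseline, below the 1.5 threshold) | no |

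Lymphocytes, white cells and electrolytes behave like the first four rows. Creatinine is mixed: the ULN multiple is kept beside the baseline multiple, so a stable raised value can still be graded. Counting only grades worse than baseline would remove each graded row above and leave the ALT/AST row unchanged.

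**2. Dilution.** Let b be the share entering at Grade 2 or higher and e the rate of new onset among the rest. If entry abnormalities are seen again after baseline, the tabulated share is b + (1 - b)e. Neither b nor e is in the documents. Take e = 5% and 20% in the two arms, a true ratio of 4.0:

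- b = 10%: 14.5% vs 28.0%, ratio 1.9
- b = 20%: 24.0% vs 36.0%, ratio 1.5
- b = 30%: 0.30 + 0.70 x 0.05 = 33.5% vs 0.30 + 0.70 x 0.20 = 44.0%, ratio 1.3
- b = 40%: 43.0% vs 52.0%, ratio 1.2

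**3. Chance imbalance with no drug effect.** Let X and Y be independent Binomial(n, p), where p is the share abnormal at entry (assumed). The table gives the exact P(|X - Y|/n >= 0.20). The documents say only that fewer than 60 will be enrolled; 29 per arm is the largest balanced size below that.

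| p | 15 per arm | 29 per arm |
|---|---|---|
| 10% | 0.121 | 0.016 |
| 20% | 0.249 | 0.070 |
| 30% | 0.318 | 0.114 |
| 40% | 0.351 | 0.140 |

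These are per test. They are lumpy in n, because 20 points is exactly 3 of 15. At 12 per arm and p = 30% the probability is 0.263, lower than at 15. The standard deviation of the difference, sqrt(2p(1 - p)/n), is smoother: at p = 30% it is 18.7 points at 12 per arm, 16.7 at 15 and 12.0 at 29.

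**The case against.** The strongest case for leaving the plan alone has four parts.

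- **Endpoint.** The SAP implements what the protocol names, and both label it post-baseline. Neither calls the counts drug-related. This stands, and it is why the maximum-grade table should be kept.
- **Liver tests.** Liver injury is a named risk of guselkumab in Protocol 2.3.1, and the liver tests already have baseline-relative grading. A reader might infer that every laboratory grade ignores entry status; for those five tests that is wrong.
- **Other summaries.** SAP 5.7.3.1 plans change from baseline by arm with box plots, Protocol 9.4.6 adds descriptive statistics at baseline, and clinically relevant laboratory changes are recorded as adverse events. A stable participant contributes zero change, and a baseline imbalance in an analyte can be seen. This helps, but group summaries do not show whether a particular graded participant worsened.
- **No inference.** No between-arm test of grades is planned, and randomization favors neither arm on expectation. Both are correct. A reader might infer a bias against guselkumab; the documents do not support that.

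One more tempting inference is that the SAP applies a stricter rule to vital signs and dropped it for laboratories. SAP 5.7.3.3 does plan "Summaries of treatment-emergent abnormal vital signs during intervention", but it requires only a baseline and a post-baseline assessment. It states no condition of worsening, and its limits for pulse and blood pressure are absolute. The contrast is one of wording and does not show an inconsistent rule.

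**Conclusion.** The point holds for tests graded on absolute, LLN or ULN limits: hemoglobin, neutrophils, platelets, lymphocytes, white cells, albumin, electrolytes and, in part, creatinine. For these, permitted entry abnormalities are counted with new ones, and no planned output sets baseline grade beside worst grade.

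The overlap between entry limits and grade limits is certain from the documents. Its size is not, because it depends on the share abnormal at entry, which they do not give. Over an assumed 10% to 40%, entry status alone produces a gap of 20 points or more with probability 12% to 35% at 15 per arm and 2% to 14% at 29 per arm. That calculation assumes that an entry abnormality appears at least once after baseline. Dilution depends further on the assumed new-onset rates. This is a limit on how a descriptive safety table can be read; it does not invalidate the safety analysis.

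**What to change.** In SAP 5.7.3.1, keep the maximum-grade summary and add, by arm, a shift table of baseline grade by worst post-baseline grade, with the number of participants whose grade worsened from baseline. In the Grade 2 or higher listing, add a column for baseline grade and mark values already at that grade at entry. Adding rather than replacing leaves the protocol-named endpoint intact; a rule that counted only worsened grades in its place would change that endpoint.

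The cost is a few tables from data already collected and graded under Appendix 10, at the single database lock. The downside is slightly longer output.

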5.7.3.2. Electronic Columbia-Suicide Severity Rating Scale

The Electronic Columbia-Suicide Severity Rating Scale (eC-SSRS) will be used as a screening tool to prospectively evaluate suicidal ideation and behavior among study participants. The eC-SSRS measures 5 possible levels of suicidal ideation and 4 possible suicidal behaviors, as well as non-suicidal self-injurious behavior. The assessment is a fully-structured, participant self-report eC-SSRS questionnaire, including standardized questions, follow-up prompts, error handling routines, and scoring conventions (Mundt JC, et al, 2013; Posner K, et al, 2011). Two versions of the eC-SSRS will be used in this study, the *Lifetime* version and the *Since Last Contact* version. The *Lifetime* version will be conducted during the screening visit and the *Since Last Contact* version will be conducted at all other visits.

At the conclusion of each assessment, the eC-SSRS Findings Report can be viewed electronically. At screening ("In the last 6 months") and Week 0, participants with an Ideation level (1-5) or any suicidal behaviors or with a response of "YES" for non-suicidal, self-injurious behavior must be determined to be not at risk by the investigator based on an evaluation by a mental health professional in order to be randomized. Participants with an Ideation level (1-5) on the eC-SSRS or any suicidal behaviors or with a response of "YES" for non-suicidal, self-injurious behavior at any postbaseline visit will also be referred to an appropriate mental health professional for evaluation. If a participant's psychiatric disorder can be adequately treated with psychotherapy and/or pharmacotherapy then the participant, at the discretion of the investigator, should be continued with treatment. Ultimately, the determination of suicidality and risk is up to the investigator's clinical judgment following evaluation by a mental health professional (eg, psychiatrist, psychologist, or appropriately trained social worker or nurse).

The eC-SSRS Findings Report will be summarized by intervention group for each finding: Ideation 1-5, and Behaviors (Actual (non-fatal and completed), Interrupted, Aborted and Preparatory attempts).

5.7.3.3. Vital Signs and Physical Examination Findings

Continuous vital sign parameters including weight, height, pulse, and blood pressure (systolic and diastolic) will be summarized at each assessment time point. Change from baseline of the vital sign parameters will be summarized for through Week 24 and through Week 60. Descriptive statistics (mean, SD, median, minimum and maximum) will be presented.

Summaries of treatment-emergent abnormal vital signs during intervention, as defined in Table 4, will be provided for participants who had a baseline assessment and at least 1 postbaseline assessment for that vital sign. A listing of participants with treatment-emergent abnormal vital signs will be presented.

Table 4: Abnormal Vital Sign Parameters

Vital Sign	Criteria
Pulse	>130 bpm or <50
Systolic blood pressure	>180 mm Hg or <85 mm Hg
Diastolic blood pressure	>115 mm Hg or <55 mm Hg
Weight	Increase/decrease 10 kg from baseline

5.8. Other Analyses

Early Termination Note: Due to the Sponsor's decision to stop screening of new participants as a result of enrollment challenges, fewer than 60 participants will be enrolled in the study. The end of study will occur after all enrolled participants have completed the Week 20 visit or discontinued study intervention prior to Week 24, and all participants have completed their final efficacy and safety visits per the SoA.

For the CSR, PK Active Study Intervention serum concentration over time will be summarized and displayed graphically. Antibodies to guselkumab status over time will be summarized and a listing of participants positive for antibodies to guselkumab may be presented when appropriate. All other analyses that are specified in this section will not be reported in the CSR.

5.8.1. Pharmacokinetics

PK analyses will be performed on the PK analysis set, defined as participants who have received at least 1 dose of Active Study Intervention and have at least 1 post initial dose blood sample drawn for PK analysis.

If anti-Active Study Intervention antibodies are detected in certain participants, PK parameters may be summarized with and without these participants.

Descriptive statistics (N, mean, SD, median, range, and IQ range) will be used to summarize Active Study Intervention/Analyte serum concentrations at each sampling time point. PK data will be displayed graphically, such as mean +/- SD PK concentrations over time by intervention group.

Active Study Intervention concentrations below the lower limit of quantification×minimum required dilution will be imputed as zero in the summary statistics.

Active Study Intervention concentrations will be presented based on baseline body weight quartiles at each time point.

PK data may be displayed graphically, such as mean +/- SD PK concentrations over time by weight group.

If sufficient data are available, then population PK analysis using serum concentration-time data of Active Study Intervention will be performed using nonlinear mixed-effects modeling. Details will be given in a population PK analysis plan and the results of the analysis will be presented in a separate report.

Urine/PK concentration will be summarized in a separate report.

5.8.2. Immunogenicity

“Sample ADA status” and sample titer as well as the cumulative “participant ADA status” and peak titer through the visit will be coded and provided by the bioanalytical group.

Participants evaluable for immunogenicity are defined as having at least one postdose anti-drug antibody (ADA) time point collected for anti-guselkumab antibody detection.

Participants with treatment-emergent anti-guselkumab antibodies include participants with treatment-induced anti-guselkumab antibodies and treatment-boosted anti-guselkumab antibodies.

Participants with treatment-induced anti-guselkumab antibodies have an anti-guselkumab antibodies negative sample prior to guselkumab administration and at least one anti-guselkumab antibodies positive sample after guselkumab.

Participants with treatment-boosted anti-guselkumab antibodies have an anti-guselkumab antibodies positive sample prior to guselkumab administration and at least one anti-guselkumab antibodies positive sample after guselkumab with a [2]-fold increase in titer over baseline.

In participants who have a positive sample prior to guselkumab administration, if titer remains the same after intervention or if ADA titer reduces or ADA disappears, the participant is classified as “treatment-emergent ADA negative”. Participants that are unavailable for treatment-emergent ADA following intervention will be classified as “participants with baseline samples only”, ie, no appropriate sample is available after intervention.

The anti-guselkumab antibodies summary and analysis will be based on the observed data; therefore no imputation of missing data will be performed. Note: participant status is through each visit, thus, participant status and peak titers may change as the study progresses over time. Therefore, the ‘participant ADA status’ at a visit represents the cumulative ADA status through that visit. For example, if a study has a lock at Week 24, datasets through Week 24 will have participant level status (eg, negative) but at Week 52, they may have developed ADA and the

participant status becomes “treatment-emergent ADA positive” from the interim to the final DBL. Peak titers can also change (increase) if a higher titer occurs after an initial DBL.

The summary of participants with baseline positive samples is taken from the sample status at baseline. There is no participant level status at baseline.

Incidence of antibody (evaluable, treatment-emergent ADA positive, treatment-emergent ADA negative) status and neutralizing antibodies to guselkumab will be summarized by intervention group.

In addition, listings of participants with baseline positive ADA samples, participants who are classified as positive for treatment-emergent anti-guselkumab antibodies and participants who discontinue the study by anti-guselkumab antibodies status as well as graphical representation of median serum guselkumab concentration by antibody status may be presented.

The Peak Titer for participants positive for treatment-emergent anti-guselkumab antibodies will be grouped by Peak Titer categories. Example: $\leq 1:10$, 10 to 100, 100 to 1000, >1000 , if needed.

Incidence of treatment-emergent positive antibody across Peak Titer categories might be summarized.

Descriptive statistics (N, mean, SD, median, range, and IQ range) and incidence (N, %) of the relationship between treatment-emergent anti-guselkumab antibodies status (positive or negative) and PK concentration will be assessed.

Participants in response (N, %) for treatment-emergent anti-guselkumab antibodies status (positive or negative) and efficacy endpoints will be assessed:

- Participants evaluable for immunogenicity
- Efficacy endpoints repeated for different levels of response (eg, proportion of participants achieving at least 50% decrease in proteinuria from baseline at Week 24, proportion of participants achieving complete renal response (CRR) at Week 52 and change in UPCR)
 - Number of participants (N)
 - Participants in response (N, %)

Incidence (N, %) between treatment-emergent anti-guselkumab antibodies status (positive or negative) and infusion-related reactions will be assessed:

- Participants evaluable for immunogenicity
- Participants with infusion-related reaction
- Participants with severe infusion-related reaction
- Participants with serious infusion-related reaction
- Participants with infusion-related reaction leading to discontinuation

- Guselkumab infusions with infusion-related reactions (out of total number of guselkumab infusions)
- Placebo infusions with infusion-related reactions (out of total number of placebo infusions).

Incidence (N, %) between treatment-emergent anti-guselkumab antibodies status (positive or negative) and injection site reactions will be assessed:

- Participants evaluable for immunogenicity
- Participants with injection site reaction
- Participants with severe injection site reaction
- Participants with serious injection site reaction
- Participants with injection site reaction leading to discontinuation
- Guselkumab injections with injection site reactions (out of total number of guselkumab injections)
- Placebo injections with injection site reactions (out of total number of placebo injections).

